Visual inspection of histograms and D'Agostino–Pearson's normality tests will be used to assess continuous distribution of the data. For the conventional ventilation and INTELLiVENT-ASV arms, the baseline characteristics will be expressed as counts and percentages, means and standard deviations (SD), or medians and interquartile ranges (IQR) whenever appropriate. Hypothesis tests will be two-sided with a significance level of 5%. We will not adjust P -values for multiple comparisons. Analyses will be performed using the R (R Core Team, 2016, Vienna, Austria) program.

Trial profile: Patient flows will be presented in a CONSORT flowchart (Figure 1).

Baseline comparisons: Patient's baseline characteristics will be presented by study arm (eTable 2).

Adherence to study interventions and, ventilator variables and vital signs:

Ventilatory variables and vital signs will be reported from ICU admission until extubation or up to the first 72hours of recorded mechanical ventilation time (eTable 3). These variables, including driving pressure and mechanical power, will be compared among the groups using Student's *t* test. Also, the trend of the ventilator variables every 30 minutes for the first three hours will be compared between the groups using mixed-effect linear models, considering an interaction term between time and group and the patients as random effects.

Outcomes:

Percentage of time in the optimal, acceptable and unacceptable zone for at least 30 seconds during the first three hours of ventilation or until extubation, if extubated earlier, and according to the postoperative total recorded ventilation time (eTable 4).

The number of episodes where the ventilation stays in one of the three zone for at least 30 consecutive seconds will be calculated. Then, this number will be corrected by the total duration of ventilation as:

$$\%_{UZ} = (T_{UZ} / DV) \times 100$$

Where $\%_{UZ}$ is the percentage of time in a zone, T_{UZ} is the time in seconds where the ventilation stays in the specific zone for at least 30 consecutive seconds, and DV is the total duration of ventilation in seconds. This number will be reported as mean \pm standard deviation and median (interquartile range). The effect of the intervention will be estimated with a Student's *t*-test and reported as the mean difference between the two groups. The consistency of the findings of the Student's *t*-test will be tested using a bootstrapped Student's *t*-test with 1,000

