Patients that died or had a re-sternotomy (for example due to bleeding) during the first three hours (for the first three hours per protocol analysis) or during the logging of the datalogger (for the overall recorded per protocol analysis) will be excluded for the per-protocol analysis of the primary outcome.

As treated analysis: In creating a as treated analysis we will analyze the recorded ventilation data according to the treatment they actually received. Patients receiving the mode of the group that they were not assigned to will be excluded for the per-protocol analysis of the primary outcome.

Subgroup analyses: Treatment effects on the primary outcome will be analyzed according to the following subgroups: 1) patient who were successfully extubated before or after the median postoperative mechanical ventilation time (eTable 6); 2) subgroup analysis based on the intraoperative mechanical ventilation time: shorter or longer than the median intraoperative mechanical ventilation time (eTable 7); 3) patients with $\text{PaO}_2 / \text{FiO}_2$ below or above the median $\text{PaO}_2 / \text{FiO}_2$

at admission on the ICU (eTable 8); The effects on subgroups will be evaluated according to the interaction effects between each subgroup and the study arms by generalized linear models considering zero-inflated distributions and presented in a forest plot.

CONCLUSION

According to best research practice, we reported here the pre-specified detailed statistical analysis plan prior to locking the database and starting analyses. This document guarantees against reporting bias, selective reporting and data-driven results, as such enhancing the utility of the reported results.

TABLES

eTable 1

Predefined zones of ventilation

	Optimal	Acceptable*	Not acceptable*
Tidal volume (ml/kg PBW)	6-8 (proposed 4-8)	>8-12	>12
EtCO ₂ (mmHg)	30-45	<30-25 >45-50	<25 ≥51
Peak pressure (cmH ₂ O)	≤30	31-35	>35
SpO ₂ (%)	93-98 (≥93 if FIO ₂ <40%)	93-85 ≥98	<85

*for analysis calculated as lasting >30 seconds and per breathing.

eTable 2 – Baseline characteristics of the patients

	INTELLiVENT- ASV	Conventional ventilation
Age, years	Mean \pm SD	Mean \pm SD
Male sex	N / Total (%)	N / Total (%)
BMI, kg/m ²	Mean \pm SD	Mean \pm SD
PBW, kg	Mean \pm SD	Mean \pm SD
SAPS II score	Mean \pm SD	Mean \pm SD
APACHE IV score	Mean \pm SD	Mean \pm SD
Euroscore II	Mean \pm SD	Mean \pm SD
Tobacco use	N / Total (%)	N / Total (%)
History of alcohol abuse	N / Total (%)	N / Total (%)

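### Effect modification by admission PaO2/FiO2 and by intraoperative ventilation time is tested only after a median split, which discards information; the scale of the interaction test is also left open

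*Combined protocol and SAP*

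**What the plan says.** Under *Subgroup analyses* the SAP states: "Treatment effects on the primary outcome will be analyzed according to the following subgroups". Three subgroup variables follow, each dichotomised at its median: time to successful extubation (eTable 6), intraoperative ventilation time, described as "shorter or longer than the median intraoperative mechanical ventilation time" (eTable 7), and PaO2/FiO2 at ICU admission (eTable 8).

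On the test it states: "The effects on subgroups will be evaluated according to the interaction effects between each subgroup and the study arms". The tool is "generalized linear models considering zero-inflated distributions", with the results shown in a forest plot. The paragraph names no family, no link, no rule for which part of a zero-inflated model supplies the p-value, and no scale for the forest plot.

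The main analysis of percentage of time in a zone, under *Outcomes*, is a Student's t-test "reported as the mean difference between the two groups". If the data prove strongly asymmetric, the best-fitting distribution is used instead. The shells of eTables 6 to 8 give a mean difference as the effect estimate. As they read, they have no separate columns for the two halves of a subgroup and no interaction p-value.

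**The concern.** PaO2/FiO2 and intraoperative ventilation time are continuous. A median split treats a patient just above the median like one far above it, and patients on either side of the median as different. If the treatment effect changes steadily with the modifier, the split test has less power than a test on the variable itself, although the data are the same. A real change in effect is then more easily missed, and the absence of a significant interaction says less.

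The second issue is scale. A zero-inflated model commonly has a logit part for zero versus non-zero and a log-link part for the positive values, hence two interaction terms. Equal mean differences in two subgroups with different baselines are unequal ratios, and the reverse holds too. If the test is on one scale and the displayed effects on another, a reader may be told that effects differ when the displayed differences are equal, or that they do not differ when the differences are far apart.

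**Working it through.** **Inputs.** From *Sample size*: at least 196 patients, equal allocation, SD 10.0 minutes, planned difference 14.0 minutes. From the statistical analysis section: two-sided 5% tests. If all 196 are analysed, a median split gives 196/4 = 49 patients per arm-by-subgroup cell. The plan states no subgroup power and no information loss, so there is no figure of its own to reproduce here. The 196 is used only as a head count. It does not follow from its stated inputs (exact t-test: 15 per arm, 30 in total before dropout), but that is a separate matter.

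**Information lost by the split.** For a linear modifier effect, loss = 1 − r², where r is the correlation between the modifier and the above-median indicator.

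- Normal: r² = 2/π = 0.637, loss 36%.
- Uniform: loss 25%.
- Gamma, shape 9 down to 2: 38% to 45%.
- Exponential: 52%.
- Lognormal, log-SD 0.25 to 1: 40% to 73%.

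The shapes are assumptions. Ventilation times may well be right-skewed, but the documents do not say.

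**Power.** SE of the difference between two subgroup effects = 10 × √(4/49) = 2.86 minutes. Power with the split = Φ(D/2.86 − 1.96). For a continuous normal modifier the standardised effect is divided by √(2/π) = 0.798.

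- D = 7 minutes: 7/2.86 = 2.45. Split: Φ(0.49) = 69%. Continuous: 2.45/0.798 = 3.07, Φ(1.11) = 87%.
- D = 5 minutes: 5/2.86 = 1.75. Split: Φ(−0.21) = 42%. Continuous: 1.75/0.798 = 2.19, Φ(0.23) = 59%.
- D = 14 minutes, as large as the planned main effect: split already above 99%.

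**Scale, conditional on a log/logit model.** For each scenario, 1,000 trials were simulated with 49 patients per cell. The interaction was tested on mean differences (linear model, robust errors) and in a two-part model (logit for zero/non-zero, log-link gamma for positive values). Cell values and links are assumptions. Disagreement means that one approach was significant at 5% and the other was not, counting the two-part model as significant if either part was.

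| Mean % of time, conventional → INTELLiVENT-ASV | Differences (points) | Ratios | Mean-difference test significant | Positive-part test significant | Disagreement |
|---|---|---|---|---|---|
| 8→2.4 and 24→7.2 | −5.6, −16.8 | 0.30, 0.30 | 90% | 5% | 87% |
| 8→4 and 24→20 | −4, −4 | 0.50, 0.83 | 5% | 60% | 59% |
| 8→4 and 16→12 | −4, −4 | 0.50, 0.75 | 4% | 42% | 44% |

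The two scales can therefore part in either direction. With an identity link, or with the interaction computed from marginal means, this conflict does not arise.

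**The case against.** A reader might infer that the forest plot will contradict its own p-values. The documents do not support that. No link or family is stated, and the interaction model and the plot share one sentence, so the plot may well show the model's estimates on the model's scale. The eTable shells do not set an interaction p-value beside the mean differences. The SAP also pairs a generalized linear model with a mean-difference cell elsewhere: ICU length of stay under *Outcomes* and in eTable 5. Estimates may therefore be converted, or the label may be a template. The primary analysis may itself leave the t-test if the data are very asymmetric. Zero inflation is plausible for time counted only in runs of at least 30 seconds, and since no count model is named, a misfit to percentages is not shown. Whether effect modification is best judged on an additive or a relative scale is a choice on which statisticians differ. These arguments stand. What remains is that the plan does not secure a common scale.

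A reader might also take the loss as a fixed third of the information, or 0.363 × 196 = 71 patients. That holds only for a normal modifier with a linear effect. Nor is interaction power poor throughout: 69% for an interaction half the size of the planned main effect is moderate. If the effect changes at a threshold, the efficiency comparison does not apply and the split may do better.

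None of this gives a reason to rest the test on the split alone when the continuous values are already collected.

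**Conclusion.** The point holds for two of the three modifiers. Testing admission PaO2/FiO2 and intraoperative ventilation time only through median splits gives up information: 36% under normality and linearity, and 25% to 73% over the shapes tried. For a normal modifier, power falls from about 87% to about 69% for a 7-minute interaction, and from about 59% to 42% for 5 minutes. The power figures rest on the plan's SD of 10 minutes, all 196 patients analysed and a linear modifier effect.

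The scale issue is conditional. The interaction p-value could disagree with the mean differences in eTables 6 to 8 if the model works on a log or logit scale, but the documents do not establish that it will.

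The analysis is secondary, so this is a modest improvement and not a threat to the primary result. Subgroup 1, split by time to extubation, is defined after randomisation and after the allocated ventilation has begun, so treatment can affect it. Nothing proposed here cures that.

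**What to change.** For admission PaO2/FiO2 and intraoperative ventilation time, base the interaction test on a model with arm, the continuous modifier and their product, using robust or bootstrap standard errors and a prespecified check of linearity. Keep the median-split estimates for display only.

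Report the interaction on the mean-difference scale. It can come directly from a linear model. If the zero-inflated model is kept, it can come as marginal mean differences with bootstrap intervals, with family, link and the tested component or joint test named. State the forest-plot scale, and add columns for the two halves and an interaction p-value to the eTable shells, so that test and displayed effects can be read together.

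The cost is SAP wording and a few extra lines of analysis code. No new data are needed, and the SAP describes itself as written before database lock. The downside is the assumption of a roughly linear modifier effect and lower efficiency under a threshold effect; the linearity check and the retained split display would help reveal such a departure.

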Median (IQR)	Median (IQR)	Median (IQR)	Mean difference		Median (IQR)	Median (IQR)	Mean difference		Median (IQR)	Median (IQR)	Mean difference	
Unacceptable zone	Mean ± SD	Mean ± SD	Mean difference		Mean ± SD	Mean ± SD	Mean difference		Mean ± SD	Mean ± SD	Mean difference	
Median (IQR)	Median (IQR)	Median (IQR)	Mean difference		Median (IQR)	Median (IQR)	Mean difference		Median (IQR)	Median (IQR)	Mean difference	
Percentage of time* in:												
Optimal zone	Mean ± SD	Mean ± SD	Mean difference		Mean ± SD	Mean ± SD	Mean difference		Mean ± SD	Mean ± SD	Mean difference	
Median (IQR)	Median (IQR)	Median (IQR)	Mean difference		Median (IQR)	Median (IQR)	Mean difference		Median (IQR)	Median (IQR)	Mean difference	
Acceptable zone	Mean ± SD	Mean ± SD	Mean difference		Mean ± SD	Mean ± SD	Mean difference		Mean ± SD	Mean ± SD	Mean difference	
Median (IQR)	Median (IQR)	Median (IQR)	Mean difference		Median (IQR)	Median (IQR)	Mean difference		Median (IQR)	Median (IQR)	Mean difference	
Unacceptable zone	Mean ± SD	Mean ± SD	Mean difference		Mean ± SD	Mean ± SD	Mean difference		Mean ± SD	Mean ± SD	Mean difference	
Median (IQR)	Median (IQR)	Median (IQR)	Mean difference		Median (IQR)	Median (IQR)	Mean difference		Median (IQR)	Median (IQR)	Mean difference	
All recorded breaths and time												
Percentage of breaths in:												
Optimal zone	Mean ± SD	Mean ± SD	Mean difference		Mean ± SD	Mean ± SD	Mean difference		Mean ± SD	Mean ± SD	Mean difference	
Median (IQR)	Median (IQR)	Median (IQR)	Mean difference		Median (IQR)	Median (IQR)	Mean difference		Median (IQR)	Median (IQR)	Mean difference	
Acceptable zone	Mean ± SD	Mean ± SD	Mean difference		Mean ± SD	Mean ± SD	Mean difference		Mean ± SD	Mean ± SD	Mean difference	
Median (IQR)	Median (IQR)	Median (IQR)	Mean difference		Median (IQR)	Median (IQR)	Mean difference		Median (IQR)	Median (IQR)	Mean difference	
Unacceptable zone	Mean ± SD	Mean ± SD	Mean difference		Mean ± SD	Mean ± SD	Mean difference		Mean ± SD	Mean ± SD	Mean difference	
Median (IQR)	Median (IQR)	Median (IQR)	Mean difference		Median (IQR)	Median (IQR)	Mean difference		Median (IQR)	Median (IQR)	Mean difference	
Percentage of time* in:												
Optimal zone	Mean ± SD	Mean ± SD	Mean difference		Mean ± SD	Mean ± SD	Mean difference		Mean ± SD	Mean ± SD	Mean difference	
Median (IQR)	Median (IQR)	Median (IQR)	Mean difference		Median (IQR)	Median (IQR)	Mean difference		Median (IQR)	Median (IQR)	Mean difference	
Acceptable zone	Mean ± SD	Mean ± SD	Mean difference		Mean ± SD	Mean ± SD	Mean difference		Mean ± SD	Mean ± SD	Mean difference	
Median (IQR)	Median (IQR)	Median (IQR)	Mean difference		Median (IQR)	Median (IQR)	Mean difference		Median (IQR)	Median (IQR)	Mean difference	
Unacceptable zone	Mean ± SD	Mean ± SD	Mean difference		Mean ± SD	Mean ± SD	Mean difference		Mean ± SD	Mean ± SD	Mean difference	
Median (IQR)	Median (IQR)	Median (IQR)	Mean difference		Median (IQR)	Median (IQR)	Mean difference		Median (IQR)	Median (IQR)	Mean difference	

eTable 5 – Secondary outcomes	Intention-to-treat				Per-protocol			
	INTELLiVENT-ASV	Conventional mode	Effect Estimate (95% CI)	P value	INTELLiVENT-ASV	Conventional mode	Effect Estimate (95% CI)	P value
Ventilation time								
Intubation – successful extubation*	Mean ± SD Median (IQR)	Mean ± SD Median (IQR)	Mean difference		Mean ± SD Median (IQR)	Mean ± SD Median (IQR)	Mean difference	
ICU admission – successful extubation*	Mean ± SD Median (IQR)	Mean ± SD Median (IQR)	Mean difference		Mean ± SD Median (IQR)	Mean ± SD Median (IQR)	Mean difference	
Weaning time								
Stop sedation – successful extubation*	Mean ± SD Median (IQR)	Mean ± SD Median (IQR)	Mean difference		Mean ± SD Median (IQR)	Mean ± SD Median (IQR)	Mean difference	
Time until spontaneous breathing**								
Intubation – spontaneous breathing	Mean ± SD Median (IQR)	Mean ± SD Median (IQR)	Mean difference		Mean ± SD Median (IQR)	Mean ± SD Median (IQR)	Mean difference	
ICU admission – spontaneous breathing	Mean ± SD Median (IQR)	Mean ± SD Median (IQR)	Mean difference		Mean ± SD Median (IQR)	Mean ± SD Median (IQR)	Mean difference	
Stop sedation – spontaneous breathing	Mean ± SD Median (IQR)	Mean ± SD Median (IQR)	Mean difference		Mean ± SD Median (IQR)	Mean ± SD Median (IQR)	Mean difference	
Mortality								
ICU	N / Total (%)	N / Total (%)	Risk ratio		N / Total (%)	N / Total (%)	Risk ratio	
30-day	N / Total (%)	N / Total (%)	Hazard ratio		N / Total (%)	N / Total (%)	Hazard ratio	
Length of stay								
ICU	Mean ± SD Median (IQR)	Mean ± SD Median (IQR)	Mean difference		Mean ± SD Median (IQR)	Mean ± SD Median (IQR)	Mean difference	
ICU readmissions								
Readmission <72 hours after discharge	N / Total (%)	N / Total (%)	Risk ratio		N / Total (%)	N / Total (%)	Risk ratio	
Number of alarms								
First 3 hours (n/3 hours)	Mean ± SD Median (IQR)	Mean ± SD Median (IQR)	Mean difference		Mean ± SD Median (IQR)	Mean ± SD Median (IQR)	Mean difference	

All recorded time (n/hour) Median (IQR)	Mean ± SD Median (IQR)	Mean ± SD Median (IQR)	Mean difference	Mean ± SD Median (IQR)	Mean ± SD Median (IQR)	Mean difference
Times SpO₂ measurement of <85% during mechanical ventilation*						
First 3 hours (n/3 hours) Median (IQR)	Mean ± SD Median (IQR)	Mean ± SD Median (IQR)	Mean difference	Mean ± SD Median (IQR)	Mean ± SD Median (IQR)	Mean difference
All recorded time (n/hour) Median (IQR)	Mean ± SD Median (IQR)	Mean ± SD Median (IQR)	Mean difference	Mean ± SD Median (IQR)	Mean ± SD Median (IQR)	Mean difference
Lowest measured SpO ₂ over all recorded time.	Mean ± SD Median (IQR)	Mean ± SD Median (IQR)	Mean difference	Mean ± SD Median (IQR)	Mean ± SD Median (IQR)	Mean difference
Missing measurement**: all recorded time EtCO ₂	Mean ± SD Median (IQR)	Mean ± SD Median (IQR)	Mean difference	Mean ± SD Median (IQR)	Mean ± SD Median (IQR)	Mean difference
SpO ₂	Mean ± SD Median (IQR)	Mean ± SD Median (IQR)	Mean difference	Mean ± SD Median (IQR)	Mean ± SD Median (IQR)	Mean difference
Number of interventions						
First 3 hours (n/3 hours) Median (IQR)	Mean ± SD Median (IQR)	Mean ± SD Median (IQR)	Mean difference	Mean ± SD Median (IQR)	Mean ± SD Median (IQR)	Mean difference
All recorded time (n/hour) Median (IQR)	Mean ± SD Median (IQR)	Mean ± SD Median (IQR)	Mean difference	Mean ± SD Median (IQR)	Mean ± SD Median (IQR)	Mean difference
Pulmonary complication (first 72 hours)						
Pneumonia	N / Total (%)	N / Total (%)	Risk ratio	N / Total (%)	N / Total (%)	Risk ratio
Pneumothorax	N / Total (%)	N / Total (%)	Risk ratio	N / Total (%)	N / Total (%)	Risk ratio
Atelectasis	N / Total (%)	N / Total (%)	Risk ratio	N / Total (%)	N / Total (%)	Risk ratio
Overall	N / Total (%)	N / Total (%)	Risk ratio	N / Total (%)	N / Total (%)	Risk ratio
Acceptance score						
Score (1-10) Median (IQR)	Mean ± SD Median (IQR)	Mean ± SD Median (IQR)	Mean difference	Mean ± SD Median (IQR)	Mean ± SD Median (IQR)	Mean difference

*Measurement with a quality index >50%

** Measurement with a quality index <51%

eTable 6 – Intention-to treat analysis and per protocol analysis of the percentage of breaths and time in the optimal, acceptable and unacceptable zones during the first 3 hours of postoperative mechanical ventilation or extubation, and for all recorded breaths for patient who were successfully extubated before or after the median postoperative mechanical ventilation time.

First 3 hours of mechanical ventilation	Intention-to-treat analysis					As treated analysis					Per protocol analysis				
	INTELLIVENT-ASV	Conventional mode	Effect Estimate (95% CI)	p value	INTELLIVENT-ASV	Conventional mode	Effect Estimate (95% CI)	p value	INTELLIVENT-ASV	Conventional mode	Effect Estimate (95% CI)	p value			
Percentage of breaths in:															
Optimal zone	Mean ± SD	Mean ± SD	Mean difference		Mean ± SD	Mean ± SD	Mean difference		Mean ± SD	Mean ± SD	Mean difference		Mean difference		
Median (IQR)	Median (IQR)	Median (IQR)			Median (IQR)	Median (IQR)			Median (IQR)	Median (IQR)			Median (IQR)		
Acceptable zone	Mean ± SD	Mean ± SD	Mean difference		Mean ± SD	Mean ± SD	Mean difference		Mean ± SD	Mean ± SD	Mean difference		Mean difference		
Median (IQR)	Median (IQR)	Median (IQR)			Median (IQR)	Median (IQR)			Median (IQR)	Median (IQR)			Median (IQR)		
Unacceptable zone	Mean ± SD	Mean ± SD	Mean difference		Mean ± SD	Mean ± SD	Mean difference		Mean ± SD	Mean ± SD	Mean difference		Mean difference		
Median (IQR)	Median (IQR)	Median (IQR)			Median (IQR)	Median (IQR)			Median (IQR)	Median (IQR)			Median (IQR)		
Percentage of time* in:															
Optimal zone	Mean ± SD	Mean ± SD	Mean difference		Mean ± SD	Mean ± SD	Mean difference		Mean ± SD	Mean ± SD	Mean difference		Mean difference		
Median (IQR)	Median (IQR)	Median (IQR)			Median (IQR)	Median (IQR)			Median (IQR)	Median (IQR)			Median (IQR)		
Acceptable zone	Mean ± SD	Mean ± SD	Mean difference		Mean ± SD	Mean ± SD	Mean difference		Mean ± SD	Mean ± SD	Mean difference		Mean difference		
Median (IQR)	Median (IQR)	Median (IQR)			Median (IQR)	Median (IQR)			Median (IQR)	Median (IQR)			Median (IQR)		
Unacceptable zone	Mean ± SD	Mean ± SD	Mean difference		Mean ± SD	Mean ± SD	Mean difference		Mean ± SD	Mean ± SD	Mean difference		Mean difference		
Median (IQR)	Median (IQR)	Median (IQR)			Median (IQR)	Median (IQR)			Median (IQR)	Median (IQR)			Median (IQR)		
All recorded breaths and time															
Percentage of breaths in:															
Optimal zone	Mean ± SD	Mean ± SD	Mean difference		Mean ± SD	Mean ± SD	Mean difference		Mean ± SD	Mean ± SD	Mean difference		Mean difference		
Median (IQR)	Median (IQR)	Median (IQR)			Median (IQR)	Median (IQR)			Median (IQR)	Median (IQR)			Median (IQR)		
Acceptable zone	Mean ± SD	Mean ± SD	Mean difference		Mean ± SD	Mean ± SD	Mean difference		Mean ± SD	Mean ± SD	Mean difference		Mean difference		
Median (IQR)	Median (IQR)	Median (IQR)			Median (IQR)	Median (IQR)			Median (IQR)	Median (IQR)			Median (IQR)		
Unacceptable zone	Mean ± SD	Mean ± SD	Mean difference		Mean ± SD	Mean ± SD	Mean difference		Mean ± SD	Mean ± SD	Mean difference		Mean difference		
Median (IQR)	Median (IQR)	Median (IQR)			Median (IQR)	Median (IQR)			Median (IQR)	Median (IQR)			Median (IQR)		
Percentage of time* in:															
Optimal zone	Mean ± SD	Mean ± SD	Mean difference		Mean ± SD	Mean ± SD	Mean difference		Mean ± SD	Mean ± SD	Mean difference		Mean difference		
Median (IQR)	Median (IQR)	Median (IQR)			Median (IQR)	Median (IQR)			Median (IQR)	Median (IQR)			Median (IQR)		
Acceptable zone	Mean ± SD	Mean ± SD	Mean difference		Mean ± SD	Mean ± SD	Mean difference		Mean ± SD	Mean ± SD	Mean difference		Mean difference		
Median (IQR)	Median (IQR)	Median (IQR)			Median (IQR)	Median (IQR)			Median (IQR)	Median (IQR)			Median (IQR)		
Unacceptable zone	Mean ± SD	Mean ± SD	Mean difference		Mean ± SD	Mean ± SD	Mean difference		Mean ± SD	Mean ± SD	Mean difference		Mean difference		
Median (IQR)	Median (IQR)	Median (IQR)			Median (IQR)	Median (IQR)			Median (IQR)	Median (IQR)			Median (IQR)		

*for at least 30 seconds in a zone

eTable 7 – Intention-to treat analysis and per protocol analysis of the percentage of breaths and time in the optimal, acceptable and unacceptable zones during the first 3 hours of postoperative mechanical ventilation or extubation, and for all recorded breaths for patients with a intraoperative mechanical ventilation time that was shorter or longer than the median intraoperative mechanical ventilation time.

First 3 hours of mechanical ventilation	Intention-to-treat analysis					As treated analysis					Per protocol analysis				
	INTELLIVENT-ASV	Conventional mode	Effect Estimate (95% CI)	p value	INTELLIVENT-ASV	Conventional mode	Effect Estimate (95% CI)	p value	INTELLIVENT-ASV	Conventional mode	Effect Estimate (95% CI)	p value			
Percentage of breaths in:															
Optimal zone	Mean ± SD	Mean ± SD	Mean difference		Mean ± SD	Mean ± SD	Mean difference		Mean ± SD	Mean ± SD	Mean difference		Mean difference		
Median (IQR)	Median (IQR)	Median (IQR)	Median (IQR)		Median (IQR)	Median (IQR)	Median (IQR)		Median (IQR)	Median (IQR)	Median (IQR)		Median (IQR)		
Acceptable zone	Mean ± SD	Mean ± SD	Mean difference		Mean ± SD	Mean ± SD	Mean difference		Mean ± SD	Mean ± SD	Mean difference		Mean difference		
Median (IQR)	Median (IQR)	Median (IQR)	Median (IQR)		Median (IQR)	Median (IQR)	Median (IQR)		Median (IQR)	Median (IQR)	Median (IQR)		Median (IQR)		
Unacceptable zone	Mean ± SD	Mean ± SD	Mean difference		Mean ± SD	Mean ± SD	Mean difference		Mean ± SD	Mean ± SD	Mean difference		Mean difference		
Median (IQR)	Median (IQR)	Median (IQR)	Median (IQR)		Median (IQR)	Median (IQR)	Median (IQR)		Median (IQR)	Median (IQR)	Median (IQR)		Median (IQR)		
Percentage of time* in:															
Optimal zone	Mean ± SD	Mean ± SD	Mean difference		Mean ± SD	Mean ± SD	Mean difference		Mean ± SD	Mean ± SD	Mean difference		Mean difference		
Median (IQR)	Median (IQR)	Median (IQR)	Median (IQR)		Median (IQR)	Median (IQR)	Median (IQR)		Median (IQR)	Median (IQR)	Median (IQR)		Median (IQR)		
Acceptable zone	Mean ± SD	Mean ± SD	Mean difference		Mean ± SD	Mean ± SD	Mean difference		Mean ± SD	Mean ± SD	Mean difference		Mean difference		
Median (IQR)	Median (IQR)	Median (IQR)	Median (IQR)		Median (IQR)	Median (IQR)	Median (IQR)		Median (IQR)	Median (IQR)	Median (IQR)		Median (IQR)		
Unacceptable zone	Mean ± SD	Mean ± SD	Mean difference		Mean ± SD	Mean ± SD	Mean difference		Mean ± SD	Mean ± SD	Mean difference		Mean difference		
Median (IQR)	Median (IQR)	Median (IQR)	Median (IQR)		Median (IQR)	Median (IQR)	Median (IQR)		Median (IQR)	Median (IQR)	Median (IQR)		Median (IQR)		
All recorded breaths and time															
Percentage of breaths in:															
Optimal zone	Mean ± SD	Mean ± SD	Mean difference		Mean ± SD	Mean ± SD	Mean difference		Mean ± SD	Mean ± SD	Mean difference		Mean difference		
Median (IQR)	Median (IQR)	Median (IQR)	Median (IQR)		Median (IQR)	Median (IQR)	Median (IQR)		Median (IQR)	Median (IQR)	Median (IQR)		Median (IQR)		
Acceptable zone	Mean ± SD	Mean ± SD	Mean difference		Mean ± SD	Mean ± SD	Mean difference		Mean ± SD	Mean ± SD	Mean difference		Mean difference		
Median (IQR)	Median (IQR)	Median (IQR)	Median (IQR)		Median (IQR)	Median (IQR)	Median (IQR)		Median (IQR)	Median (IQR)	Median (IQR)		Median (IQR)		
Unacceptable zone	Mean ± SD	Mean ± SD	Mean difference		Mean ± SD	Mean ± SD	Mean difference		Mean ± SD	Mean ± SD	Mean difference		Mean difference		
Median (IQR)	Median (IQR)	Median (IQR)	Median (IQR)		Median (IQR)	Median (IQR)	Median (IQR)		Median (IQR)	Median (IQR)	Median (IQR)		Median (IQR)		
Percentage of time* in:															
Optimal zone	Mean ± SD	Mean ± SD	Mean difference		Mean ± SD	Mean ± SD	Mean difference		Mean ± SD	Mean ± SD	Mean difference		Mean difference		
Median (IQR)	Median (IQR)	Median (IQR)	Median (IQR)		Median (IQR)	Median (IQR)	Median (IQR)		Median (IQR)	Median (IQR)	Median (IQR)		Median (IQR)		
Acceptable zone	Mean ± SD	Mean ± SD	Mean difference		Mean ± SD	Mean ± SD	Mean difference		Mean ± SD	Mean ± SD	Mean difference		Mean difference		
Median (IQR)	Median (IQR)	Median (IQR)	Median (IQR)		Median (IQR)	Median (IQR)	Median (IQR)		Median (IQR)	Median (IQR)	Median (IQR)		Median (IQR)		
Unacceptable zone	Mean ± SD	Mean ± SD	Mean difference		Mean ± SD	Mean ± SD	Mean difference		Mean ± SD	Mean ± SD	Mean difference		Mean difference		
Median (IQR)	Median (IQR)	Median (IQR)	Median (IQR)		Median (IQR)	Median (IQR)	Median (IQR)		Median (IQR)	Median (IQR)	Median (IQR)		Median (IQR)		

*for at least 30 seconds in a zone

[figure not shown]
eTable 8 – Intention-to treat-analysis, as treated analysis and per protocol analysis of the percentage of breaths and time in the optimal, acceptable and unacceptable zones during the first 3 hours of postoperative mechanical ventilation or extubation, and for all recorded breaths for patients with $\text{PaO}_2 / \text{FiO}_2$ below or above the median $\text{PaO}_2 / \text{FiO}_2$ at admission on the ICU.

First 3 hours of mechanical ventilation	Intention-to-treat analysis					As treated analysis					Per protocol analysis				
	INTELLIVENT-ASV	Conventional mode	Effect Estimate (95% CI)	p value	INTELLIVENT-ASV	Conventional mode	Effect Estimate (95% CI)	p value	INTELLIVENT-ASV	Conventional mode	Effect Estimate (95% CI)	p value			
Percentage of breaths in:															
Optimal zone	Mean \pm SD	Mean \pm SD	Mean difference		Mean \pm SD	Mean \pm SD	Mean difference		Mean \pm SD	Mean \pm SD	Mean difference		Mean difference		
Median (IQR)	Median (IQR)	Median (IQR)	Median (IQR)		Median (IQR)	Median (IQR)	Median (IQR)		Median (IQR)	Median (IQR)	Median (IQR)		Median (IQR)		
Acceptable zone	Mean \pm SD	Mean \pm SD	Mean difference		Mean \pm SD	Mean \pm SD	Mean difference		Mean \pm SD	Mean \pm SD	Mean difference		Mean difference		
Median (IQR)	Median (IQR)	Median (IQR)	Median (IQR)		Median (IQR)	Median (IQR)	Median (IQR)		Median (IQR)	Median (IQR)	Median (IQR)		Median (IQR)		
Unacceptable zone	Mean \pm SD	Mean \pm SD	Mean difference		Mean \pm SD	Mean \pm SD	Mean difference		Mean \pm SD	Mean \pm SD	Mean difference		Mean difference		
Median (IQR)	Median (IQR)	Median (IQR)	Median (IQR)		Median (IQR)	Median (IQR)	Median (IQR)		Median (IQR)	Median (IQR)	Median (IQR)		Median (IQR)		
Percentage of time* in:															
Optimal zone	Mean \pm SD	Mean \pm SD	Mean difference		Mean \pm SD	Mean \pm SD	Mean difference		Mean \pm SD	Mean \pm SD	Mean difference		Mean difference		
Median (IQR)	Median (IQR)	Median (IQR)	Median (IQR)		Median (IQR)	Median (IQR)	Median (IQR)		Median (IQR)	Median (IQR)	Median (IQR)		Median (IQR)		
Acceptable zone	Mean \pm SD	Mean \pm SD	Mean difference		Mean \pm SD	Mean \pm SD	Mean difference		Mean \pm SD	Mean \pm SD	Mean difference		Mean difference		
Median (IQR)	Median (IQR)	Median (IQR)	Median (IQR)		Median (IQR)	Median (IQR)	Median (IQR)		Median (IQR)	Median (IQR)	Median (IQR)		Median (IQR)		
Unacceptable zone	Mean \pm SD	Mean \pm SD	Mean difference		Mean \pm SD	Mean \pm SD	Mean difference		Mean \pm SD	Mean \pm SD	Mean difference		Mean difference		
Median (IQR)	Median (IQR)	Median (IQR)	Median (IQR)		Median (IQR)	Median (IQR)	Median (IQR)		Median (IQR)	Median (IQR)	Median (IQR)		Median (IQR)		
All recorded breaths and time															
Percentage of breaths in:															
Optimal zone	Mean \pm SD	Mean \pm SD	Mean difference		Mean \pm SD	Mean \pm SD	Mean difference		Mean \pm SD	Mean \pm SD	Mean difference		Mean difference		
Median (IQR)	Median (IQR)	Median (IQR)	Median (IQR)		Median (IQR)	Median (IQR)	Median (IQR)		Median (IQR)	Median (IQR)	Median (IQR)		Median (IQR)		
Acceptable zone	Mean \pm SD	Mean \pm SD	Mean difference		Mean \pm SD	Mean \pm SD	Mean difference		Mean \pm SD	Mean \pm SD	Mean difference		Mean difference		
Median (IQR)	Median (IQR)	Median (IQR)	Median (IQR)		Median (IQR)	Median (IQR)	Median (IQR)		Median (IQR)	Median (IQR)	Median (IQR)		Median (IQR)		
Unacceptable zone	Mean \pm SD	Mean \pm SD	Mean difference		Mean \pm SD	Mean \pm SD	Mean difference		Mean \pm SD	Mean \pm SD	Mean difference		Mean difference		
Median (IQR)	Median (IQR)	Median (IQR)	Median (IQR)		Median (IQR)	Median (IQR)	Median (IQR)		Median (IQR)	Median (IQR)	Median (IQR)		Median (IQR)		
Percentage of time* in:															
Optimal zone	Mean \pm SD	Mean \pm SD	Mean difference		Mean \pm SD	Mean \pm SD	Mean difference		Mean \pm SD	Mean \pm SD	Mean difference		Mean difference		
Median (IQR)	Median (IQR)	Median (IQR)	Median (IQR)		Median (IQR)	Median (IQR)	Median (IQR)		Median (IQR)	Median (IQR)	Median (IQR)		Median (IQR)		
Acceptable zone	Mean \pm SD	Mean \pm SD	Mean difference		Mean \pm SD	Mean \pm SD	Mean difference		Mean \pm SD	Mean \pm SD	Mean difference		Mean difference		
Median (IQR)	Median (IQR)	Median (IQR)	Median (IQR)		Median (IQR)	Median (IQR)	Median (IQR)		Median (IQR)	Median (IQR)	Median (IQR)		Median (IQR)		
Unacceptable zone	Mean \pm SD	Mean \pm SD	Mean difference		Mean \pm SD	Mean \pm SD	Mean difference		Mean \pm SD	Mean \pm SD	Mean difference		Mean difference		
Median (IQR)	Median (IQR)	Median (IQR)	Median (IQR)		Median (IQR)	Median (IQR)	Median (IQR)		Median (IQR)	Median (IQR)	Median (IQR)		Median (IQR)		

*for at least 30 seconds in a zone

FIGURE LEGENDS

Figure 1 – Flow of the patients in the POSITIVE trial

LIST OF ABBREVIATIONS

ARDS: acute respiratory distress syndrome

APACHE: Acute Physiology And Chronic Health Evaluation

CONSORT: Consolidated Standards of Reporting Trials

COPD: chronic obstructive pulmonary disease

DSMB: Data and Safety Monitoring Board

GOLD: Global Initiative for Chronic Obstructive Lung Disease

ICH-GCP: International Conference on Harmonization - Good Clinical Practice

ICU: intensive care unit

IQR: interquartile range

LOS: length of stay

PBW: predicted body weight

SAP: statistical analysis plan

SAPS: Simplified Acute Physiology Score

SBT: Spontaneous breathing trial

SD: standard deviation

DECLARATIONS

Ethics approval and consent to participate: The Medical Research Ethics Committees United (MEC-U), Nieuwegein, The Netherlands, under reference number R16.054.

Consent for publication: Not applicable.

Availability of data and material: Not applicable.

Competing interests: The authors declare that they have no competing interests.

Funding: This study is an investigator-initiated trial. The principal investigator is funded by the Catharina Hospital, Eindhoven, The Netherlands.

Authors' contributions:

[name], designed the study, the statistical analysis plan and approved the initially submitted version of this manuscript. All authors read and approved the final manuscript.

Acknowledgments: None.

REFERENCES

1. www.ClinicalTrials.gov; Identifier: NCT03180203
3. The ARDS Definition Task Force. Acute respiratory distress syndrome: the Berlin Definition. *JAMA* 2012;307:2526–33.
